2. LIST OF ABBREVIATIONS

Term	Definition / description
AE	Adverse event
ALT	Alanine aminotransferase
ANCOVA	Analysis of covariance
ANOVA	Analysis of variance
AOC3	Amine oxidase copper-containing 3
AST	Aspartate aminotransferase
ATC	Anatomical Therapeutic Chemical classification
BCVA	Best corrected visual acuity
BI	Boehringer Ingelheim
BP	Blood pressure
BRPM	Blinded report planning meeting
CARE	Clinical data Analysis and Reporting Environment
CI-DME	Center-involved diabetic macular edema
█	█
CT	Concomitant therapy
CTC	Common Terminology Criteria
CTMS	Clinical Trial Management System
CTP	Clinical trial protocol
CTR	Clinical trial report
DBLM	Database lock meeting
DBP	Diastolic blood pressure
DR	Diabetic retinopathy
DRSS	Diabetic Retinopathy Severity Score
ECG	Electrocardiogram
ECGS	ECG analysis set
EOT	End of treatment
ETDRS	Early Treatment Diabetic Retinopathy Study
EudraCT	European clinical trials database
█	█

Term	Definition / description
FAS	Full analysis set
FP	Fundus photography
HR	Heart rate in beats per minute
ICH	International Conference on Harmonization
iPD	Important protocol deviation
LLT	Lower level term
MedDRA	Medical Dictionary for Regulatory Affairs
Max	Maximum
Min	Minimum
MMRM	Mixed effects model for repeated measures
MQRM	Medical quality review meeting
[REDACTED]	[REDACTED]
NPDR	Non-proliferative diabetic retinopathy
[REDACTED]	[REDACTED]
[REDACTED]	[REDACTED]
OD	Oculus dexter; right eye
OS	Oculus sinister; left eye
OU	Oculus uterque, both eyes
PD	Protocol deviation
[REDACTED]	[REDACTED]
[REDACTED]	[REDACTED]
PPS	Per-protocol set
PR interval	ECG interval from onset of P wave to the beginning of QRS
PT	Preferred term
Q1	Lower Quartile
Q3	Upper Quartile
QRS complex	ECG term; combination of Q, R and S waves
QT interval	ECG interval from beginning of QRS complex to the end of the T wave
QTcB [msec]	QT interval, heart rate corrected per Bazetts formula
QTcF [msec]	QT interval, heart rate corrected per Fridericias formula
RAGe	Report Appendix Generator system

Term	Definition / description
[REDACTED]	[REDACTED]
REP	Residual effect period
RPM	Report Planning Meeting; formerly known as BRPM
RR interval	ECG interval from peak of an R wave to the peak of the subsequent R wave
RS	Randomized set
SAE	Serious adverse event
SBP	Systolic blood pressure
SD	Standard deviation
SMQ	Standardized MedDRA query
SOC	System organ class
SS	Screened set
TMW	Trial medical writer
TS	Treated set
TSAP	Trial statistical analysis plan
ULN	Upper limit of normal

3. INTRODUCTION

As per ICH E9 (1), the purpose of this document is to provide a more technical and detailed elaboration of the principal features of the analysis described in the protocol, and to include detailed procedures for executing this statistical analysis of the primary and secondary variables and other data.

This TSAP assumes familiarity with the Clinical Trial Protocol (CTP), including Protocol Amendments. In particular, the TSAP is based on the planned analysis specification as written in CTP Section 7 “Statistical Methods and Determination of Sample Size”. Therefore, TSAP readers may consult the CTP for more background information on the study, e.g., on study objectives, study design and population, treatments, definition of measurements and variables, planning of sample size, randomization.

Study data will be stored in a trial database within the Medidata RAVE (BRAVE) system.

The statistical analyses will be performed within the validated working environment CARE (Clinical data Analysis and Reporting Environment), including SAS_{TM} (current Version 9.4, by SAS Institute Inc., Cary, NC, USA), and a number of SAS_{TM}-based tools (e.g., macros or the analyses of adverse event (AE) data or laboratory data; Report Appendix Generator system (RAGe) for compilation/formatting of the clinical trial report (CTR) appendices).

[REDACTED]

[REDACTED]

4. CHANGES IN THE PLANNED ANALYSIS OF THE STUDY

Secondary endpoint: 2-step improvement from baseline in DRSS

Version 1.0 of the CTP stated that a logistic regression model adjusted for treatment and baseline visual acuity will be used to analyze the secondary endpoint of the proportion of patients with at least a 2-step improvement from baseline in DRSS at week 12. However, in this Phase IIa study of 100 patients, a 2-step improvement from baseline in DRSS is likely to be observed in no more than 3 patients. Given the limited amount of data expected to be available for this endpoint, these data will be summarized as the frequency and percentage of patients with improvement from baseline of 2 steps or more. Logistic regression analyses may be performed as exploratory analyses if a sufficient number of events are observed.

The description of this secondary endpoint analysis was clarified in version 2.0 of the CTP dated 18JAN2018.

Definition of Full Analysis Set (FAS)

The FAS definition will be generalized to include all subjects in the treated set who have a baseline and at least one post-baseline measurement for either DRSS or BCVA. Individual analyses will include only subjects with baseline and post-baseline measurements for the specific endpoint being analyzed.

[REDACTED]

[REDACTED]

Protocol deviations

Per “Identify and manage important protocol deviations”(001-MCS-40-413, current version [\(4\)](#)), the term important protocol deviations will be used for trial reporting instead of important protocol violations.

[REDACTED]

[REDACTED]

[REDACTED]

Assessment of COVID-19 Impact

Site disruption due to the COVID-19 pandemic in 2020 had the potential to impact trial visits for several patients prior to database lock. To assess the impact of the pandemic on this trial, several additional data summaries are planned. The proportion of patients completing treatment prior to 01MAR2020, the proportion of patients completing the trial (Week 24 or early discontinuation) before 01MAR2020, adverse events reported before and after

01MAR2020 and type of study visit completed (phone or in clinic) will be reported for relevant visits in the CTR.

5. ENDPOINT(S)

5.1 PRIMARY ENDPOINT(S)

The primary endpoint of this trial is a safety endpoint. Per CTP Section 2.1.2, the primary endpoint is:

Ocular safety of BI 1467335 as assessed by the proportion of patients with any ocular adverse events (according to Common Terminology Criteria for Adverse Events (CTCAE)) over the on-treatment period (over 24 weeks).

5.2 SECONDARY ENDPOINT(S)

5.2.1 Key secondary endpoint(s)

This section is not applicable as there are no key secondary endpoints in this trial.

5.2.2 Secondary endpoint(s)

As defined in CTP Section 2.1.3, the secondary endpoints of this trial are:

[figure not shown]
- *Improvement of at least 2 steps on the DRSS in the study eye at week 12 compared to baseline.*
- *Adverse events other than ocular adverse events over the on-treatment period (over 24 weeks), according to CTCAE.*

DRSS levels for an individual eye are defined in [Table 5.2.2: 1](#).

Table 5.2.2: 1 Diabetic Retinopathy Severity Score (DRSS) levels – individual eye

Step	DRSS	DRSS Severity
1	10	DR Absent
2	15	DR Questionable
3	20	Microaneurysm only
4	35	Mild NPDR
5	43	Moderate NPDR
6	47	Moderately Severe NPDR
7	53	Severe NPDR
8	60	PDR

1 Higher DRSS and step values indicate more severe diabetic retinopathy.

6. GENERAL ANALYSIS DEFINITIONS

6.1 TREATMENT(S)

Treatments used in this trial are described in [Table 6.1:1](#). For basic information on treatments to be administered in this trial and the assignment of treatment arm, see CTP Section 4.

Table 6.1: 1 Treatment descriptions

Long Name	Short Name
Placebo	Placebo
BI 1467335 10 mg QD	10 mg QD

The trial periods defined in [Table 6.1:2](#) will be used for analysis of trial data.

Table 6.1: 2 Trial periods

Trial Period	Start time	Stop time
Screening	Date of informed consent	Date of first treatment administration (Visit 2a) – 1 day
On-treatment (treatment period + residual effect period)	Date of first treatment administration (Visit 2a)	Date of individual patient's end of trial participation

For this trial, the residual effect period (REP), as defined in the CTP Section 5.2.6.2, is considered the entire period from the date of last administration of trial medication until the individual patient's end of trial date. The statistical analysis and reporting of treatment-emergent adverse events will include all adverse events occurring or worsening during the on-treatment period which includes residual effect period (REP).

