### 7.3.4 Safety analyses

All findings noticed at ophthalmological examinations and/or clinically relevant symptoms (according to the judgment of the investigator) which are reported by the patients will be recorded as ocular adverse events according to the CTCAE classification. All adverse events will be coded using the Medical Dictionary for Drug Regulatory Activities (MedDRA).

Standard BI summary tables and listings will be produced. Consistent with the REP definition in [Section 5.2.6.2.1](#), all adverse events with an onset between start of treatment and last follow up visit will be assigned to the on-treatment period for evaluation. Measurements (such as ECG, vital signs, or laboratory parameters) or AEs will be assigned to treatments (see [Section 4.1](#)) based on the actual treatment at the planned time of the measurement or on the recorded time of AE onset (concept of treatment emergent AEs). Therefore, measurements planned or AEs recorded prior to first intake of trial medication will be assigned to 'screening' and those between first trial medication intake until the last follow up visit will be assigned to the treatment period. These assignments including the corresponding time intervals will be defined in detail in the TSAP.

All treated patients will be included in the safety analysis. In general, safety analyses will be descriptive in nature and will be based on BI standards. No hypothesis testing is planned.

Statistical analysis and reporting of adverse events will concentrate on treatment-emergent adverse events, i.e. all adverse events occurring between start of treatment and last follow up visit. Adverse events that start before first drug intake and deteriorate under treatment will also be considered as 'treatment-emergent'.

Frequency, severity, and causal relationship of adverse events will be tabulated by system organ class and preferred term after coding according to the current version of the Medical Dictionary for Drug Regulatory Activities (MedDRA) at the database lock. This also includes the primary endpoint.

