FU3	EOT + 84	Date of drug intake in EOT visit +63	Last assessment date	Follow-up 3

b Day 1 is defined as the date of first treatment administration

c Baseline data must be collected before time of study drug administration during Visit 2.

Table 6.7: 2 Visit intervals for ECG, vital signs, and laboratory data

		Interval Definition		
Visit	Planned day	From (day)	To (day)	Visit description
1	-28 to -3	NA	-1	Screening ^a
2a	1	1 ^b (pre-dose)	1	Baseline ^{a,c}
2a	1	1 (post-dose)	14	Week 1 ^d
3	29	15	43	Week 4
4a	57	44	71	Week 8
EOT	85	72	Date of drug intake in EOT visit +1	Week 12
FU1	EOT +28	Date of drug intake in EOT visit +2	Date of drug intake in EOT visit +34	Follow-up 1 ^e
FU2	EOT +56	Date of drug intake in EOT visit +35	Date of drug intake in EOT visit +62	Follow-up 2
FU3	EOT + 84	Date of drug intake in EOT visit +63	Last assessment date	Follow-up 3

a Baseline ECG data are collected at screening visit.

b Day 1 is defined as the date of first treatment administration.

c Baseline data must be collected before time of study drug administration during Visit 2.

d Only measurements collected after drug administration at Visit 2a are considered Week 1 values.

e In case of premature treatment discontinuation FU starts at +1 day after last drug admin for these values.

Table 6.7: 3 Visit intervals for vital signs and laboratory data for patients from sites in Spain only

Interval Definition				
Visit	Planned day	From (day)	To (day)	Visit description
1	-28- -3	NA	-1	Screening
2a	1	1 ^a	1	Baseline ^b
2b	8	1 ^c	11	Week 1 (Day 8)
2c	15	12	22	Week 2 (Day 15)
3	29	23	40	Week 4 (Day 29)
3c	50	41	53	Week 6 (Day 50)
4a	57	54	70	Week 8 (Day 57)
4b	83	71	84	Week 11 (Day 83)
EOT	85	85	Date of drug intake in EOT visit +1	Week 12 (Day 85)
FU1		Date of drug intake in EOT visit +2	Date of drug intake in EOT visit +34	Follow-up 1 ^d
FU2		Date of drug intake in EOT visit +35	Date of drug intake in EOT visit +62	Follow-up 2
FU3		Date of drug intake in EOT visit +63	Last assessment date	Follow-up 3

a Day 1 is defined as the date of first treatment administration

b Baseline data must be collected before time of study drug administration during Visit 2.

c Measurements collected after drug administration at Visit 2a or at Visit 2b are considered Week 1 values.

d In case of premature treatment discontinuation FU starts at +1 day after last drug admin for these values.

[figure not shown]

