7.8.1 Adverse events

Unless otherwise specified, the analyses of AEs will be descriptive. All analyses of AEs will be based on the number of patients reporting an AE and not on the number of events. The reporting and analyses of AEs will follow the BI guideline for analyses and presentation of adverse event data (12). All AEs will be coded using the most current version of the Medical Dictionary for Drug Regulatory Activities (MedDRA) at the time of database lock. The intensity of AEs will be classified according to the Common Terminology Criteria for Adverse Events (CTCAE) version 4.03.

For analysis, multiple AE occurrences will be collapsed into one event if all of the following conditions apply:

- All AE attributes are identical (LLT, intensity, action taken, therapy required, seriousness, reason for seriousness, relationship, outcome, AE of special interest).
- Reported occurrences are time-overlapping or time-adjacent, where time-adjacency of 2 occurrences exists if the second occurrence started on the same day or on the day after the end of the first occurrence.

The analyses of AEs will be based on the concept of treatment emergent adverse events. Consistent with the REP definition provided in [Section 6.1](#), all AEs with onset dates between the date of first treatment administration and date of last follow-up will be assigned to the randomized treatment. All AEs occurring before first treatment administration will be assigned to screening. For details on the treatment definition, see [Section 6.1](#).

According to ICH E3 ([13](#)), AEs classified as ‘other significant’ need to be reported and will include those non-serious and non-significant adverse events with (i) ‘action taken = discontinuation’ or ‘action taken = reduced’, or (ii) marked hematological and other lab abnormalities or which lead to significant concomitant therapy as identified by the Clinical Monitor/Investigator at an MQRM.

An overall summary of AEs will be presented. This summary will include the following event categories:

- All AEs
- Drug-related AEs
- AEs leading to treatment discontinuation
- Serious AEs (SAEs)
- AESI
- Highest CTC grade
- Ocular AEs

The frequency and percentage of patients with AEs will be summarized by treatment, primary system organ class (SOC), and preferred term (PT) in each of the following tables:

- All AEs
- Drug-related AEs
- AEs leading to treatment discontinuation
- Drug-related AEs leading to treatment discontinuation
- SAEs

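### SAP Table 6.1:2 and SAP 7.8.1 give pre-dose Day 1 adverse events two conflicting period assignments, so a baseline eye finding can enter the primary endpoint

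*SAP*

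**What the plan says.** SAP 6.1, Table 6.1:2, defines two periods that "will be used for analysis of trial data". Screening stops at "Date of first treatment administration (Visit 2a) – 1 day". The on-treatment period starts on the date of first administration and runs to the end of the patient's participation. Both limits are calendar dates.

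SAP 7.8.1 gives two rules for adverse events (AEs), one after the other:
- The first goes by calendar date: "all AEs with onset dates between the date of first treatment administration and date of last follow-up will be assigned to the randomized treatment".
- The second goes by order relative to the first dose: "All AEs occurring before first treatment administration will be assigned to screening".

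Protocol 7.3.4 places the split at first intake. The period that "measurements planned or AEs recorded prior to first intake of trial medication will be assigned to" is screening, and assignment rests on the recorded time of onset. It leaves the detailed intervals to the SAP.

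The flow chart schedules ophthalmological examination, fundus photography and AE collection at Visit 2a, which is Day 1. The footnotes to the visit-interval tables in SAP 6.7 say: "Baseline data must be collected before time of study drug administration during Visit 2". The primary endpoint is the proportion of patients with any ocular AE in the on-treatment period (SAP 5.1). SAP 7.8.1 takes ocular AEs as flagged by the investigator and adds a Kaplan-Meier plot of time to first ocular event after first dose.

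**The concern.** A finding can be new since screening, first noted at the pre-dose Visit 2a examination, and entered with Day 1 as its onset date. Table 6.1:2 and the onset-date sentence make it treatment-emergent. The following sentence and protocol 7.3.4 make it a screening event. The SAP does not say which rule prevails, so programming would decide.

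The endpoint is binary, so one such event makes the patient a case, and a genuine first post-dose ocular AE in the same patient then adds nothing. In the Kaplan-Meier plot the event would appear as a step on Day 1 and remove the patient from the risk set before any drug effect was possible.

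The issue is confined to new AEs that start on Day 1 before dosing. AEs that start earlier and worsen under treatment are treatment-emergent by protocol 7.3.4 and are not in question.

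**Working it through.** **1. The rules applied to one event: new ocular AE, onset date Day 1, onset before the first tablet.**

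| Source | Criterion | Period |
|---|---|---|
| SAP Table 6.1:2 | calendar date | on-treatment |
| SAP 7.8.1, onset-date sentence | calendar date | on-treatment |
| SAP 7.8.1, next sentence | before first administration | screening |
| Protocol 7.3.4 | first intake, recorded onset time | screening |

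The event satisfies both SAP sentences at once.

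**2. Can such an event arise?**
- AE collection starts at consent (protocol 5.2.6.2.1).
- Eye-examination findings are recorded as ocular AEs (protocol 7.3.4).
- Only abnormalities present before trial inclusion are baseline conditions (protocol 5.2.6.1.1).
- Visit 2a falls 3 to 28 days after Visit 1 (protocol 6.2.1), so something new can be seen.

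The route exists. It is narrow, because the eyes were already examined at screening.

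**3. Does the SAP split Day 1 elsewhere?** Yes. Table 6.7:2 separates pre-dose from post-dose on Day 1 for ECG, vital signs and laboratory data, and SAP 6.7 defines general baseline by date and time of first administration. AEs have no such split.

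**4. Are the data there to order events?** The date and time of on-site dosing are recorded in the eCRF (protocol 4.1.4.1). For AEs, protocol 8.3.1 lists onset date as mandatory and does not list a clock time, although protocol 7.3.4 refers to a recorded time of onset. Whether onset time is captured is therefore not settled by the documents.

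**5. Size, by illustration only.** No figure in the plan depends on this point, and the documents give no ocular AE rates. Let p be the true post-dose proportion and q the share of patients with a pre-dose ocular AE dated Day 1. Assume q is equal in both arms and independent of later events. Then

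observed = 1 − (1 − p)(1 − q) = p + q(1 − p).

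The observed risk difference is (1 − q) times the true one. Example with p = 20% and 35%, q = 5%: 0.20 + 0.05 × 0.80 = 0.240; 0.35 + 0.05 × 0.65 = 0.3825.

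| Assumed placebo / active | q | Observed | Difference (points) | Ratio |
|---|---|---|---|---|
| 10% / 20% | 0 | 10.0% / 20.0% | 10.0 | 2.00 |
| | 2% | 11.8% / 21.6% | 9.8 | 1.83 |
| | 5% | 14.5% / 24.0% | 9.5 | 1.66 |
| | 10% | 19.0% / 28.0% | 9.0 | 1.47 |
| 20% / 35% | 0 | 20.0% / 35.0% | 15.0 | 1.75 |
| | 2% | 21.6% / 36.3% | 14.7 | 1.68 |
| | 5% | 24.0% / 38.3% | 14.3 | 1.59 |
| | 10% | 28.0% / 41.5% | 13.5 | 1.48 |

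In the 20% / 35% case, q = 5% adds 50 × 0.05 × 0.80 = 2.0 cases on placebo and 50 × 0.05 × 0.65 = 1.6 on active, out of 50 per arm.

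**The case against.** The strongest reply is that the AE section already resolves the matter. SAP 7.8.1 states that pre-dose AEs belong to screening, protocol 7.3.4 agrees, the SAP says it is based on protocol Section 7, and the visible part of SAP Section 4 announces no change to AE assignment. The closing reference to SAP 6.1 is for the treatment definition and is not clearly meant to override. All of this stands as evidence of intent. It does not remove the conflict: Table 6.1:2 is the period definition that SAP 6.1 ties to treatment-emergent AEs, and the onset-date sentence repeats it.

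Other points also stand:
- The sponsor's AE guidelines cited in the SAP may cover same-day onset; they cannot be checked here.
- Trial inclusion is undefined in protocol 5.2.6.1.1. If it means randomization, fewer findings are exposed.
- Some patients with a relevant new study-eye finding may fail the eligibility check at Visit 2a and never be dosed.
- The analysis is descriptive with no hypothesis test, and no decision rule in the visible text depends on the count.
- Where order is unknown, counting Day 1 as on-treatment is a cautious default for a safety endpoint.

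A reader might infer that the SAP has decided to count pre-dose findings, that pre-treatment eye findings cluster on Day 1, or that the rule biases the comparison toward one arm. None of these is supported. The SAP contradicts itself on the first. Nothing shows clustering on Day 1, and the screening visit is at least as plausible a date. Pre-dose events cannot depend on treatment, so randomization should balance them.

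**Conclusion.** The conflict is real and touches the primary endpoint. Two SAP rules put all of Day 1 on-treatment, while a third SAP sentence and the protocol put pre-dose AEs in screening, so a pre-dose ocular AE dated Day 1 can be counted. The expected consequence is similar inflation of both arms and slight dilution of the contrast, with no directional bias. Its size cannot be derived from the documents and is probably small. Under equal and independent q, the risk difference shrinks by the fraction q; the ratio moves more, but the SAP plans frequencies and percentages for ocular AEs and does not name a ratio. The conclusion rests on such findings being entered as AEs with a Day 1 onset, which the documents permit but do not quantify.

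**What to change.** - In SAP Table 6.1:2, end screening and start the on-treatment period at the date and time of first administration.
- Reword the onset-date sentence in SAP 7.8.1 so that it agrees with the sentence after it and with protocol 7.3.4.
- Classify Day 1 AEs as pre- or post-dose from the recorded onset time where it is held. Otherwise use masked review or a query before database lock, against the recorded dosing time.
- Count Day 1 AEs whose order cannot be determined as on-treatment, and report the ocular AE count with and without them. Apply the same classification to the Kaplan-Meier plot.

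No new eCRF field is needed, and one would come late: the SAP is dated 29 June 2020 and described as final before database lock. The review can use the masked report planning meeting that SAP 6.2 already foresees. The cost is two wording changes and a few queries or masked reviews.

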6.2 IMPORTANT PROTOCOL DEVIATIONS

A protocol deviation (PD) is important if it affects the rights or safety of the study subjects, or if it can potentially influence the primary outcome measurement(s) in a non-negligible way.

A list of important PDs (iPD) for this trial is given [Table 6.2: 1](#). Important PDs will be reviewed at Medical Quality Review Meetings (MQRM) conducted periodically during the trial. Other iPDs identified during MQRMs, Blinded Report Planning Meetings (BRPM), or during review of BI CTMS issues reports may supplement this list. The decision to exclude

subjects with certain iPDS from analyses will be finalized at the last BRPM prior to database lock.

Table 6.2: 1 Important protocol violations

Category / Code	Description	Comment	Excluded from
A	Entrance criteria not met		
A1	Inclusion criteria not met		
A1.1	Age at enrollment <18 years	Inclusion criterion 1 not met or age <18 years on demographics eCRF	None
A1.2	Female patient of childbearing potential not using required contraception	Inclusion criterion 2 not met	None
A1.3	No diagnosis of Type 1 or Type 2 diabetes	Inclusion criterion 3 not met	PPS
A1.4	HbA1c > 12% at screening	Inclusion criterion 4 not met	None
A1.5	Diagnosis of NPDR without CI-DME at screening not met	Inclusion criterion 5 not met	PPS
A1.6	BCVA ETDRS letter score < 70 letters in each eye at screening	Inclusion criterion 6 not met	PPS
A1.7	Inadequate retinal examination parameters	Inclusion criterion 7 not met	PPS
A2	Exclusion criteria met		
A2.1	Additional eye disease in the study eye that may compromise visual acuity	Exclusion criterion 1 met	PPS
A2.2	Active CI-DME and OCT central subfield thickness > 300 µm in study eye	Exclusion criterion 2 met	PPS
A2.3	Anterior segment and vitreous abnormalities in the study eye	Exclusion criterion 3 met	PPS
A2.4	Evidence of neovascularization in the study eye	Exclusion criterion 4 met	PPS
A2.5	Prior pan-retinal photocoagulation in the study eye	Exclusion criterion 5 met	PPS
A2.6	History of DME or DR treatment: macular laser within 3 months prior to screening, intraocular injections within 6 months prior to screening, or >4 prior injections in study eye	Exclusion criterion 6 met	PPS
A2.7	Treatment with MAO inhibitors or drugs with potential side effects due to MAO inhibition	Exclusion criterion 7 met	None
A2.8	Current or planned use of restricted medications	Exclusion criteria 8 or 9 met	PPS
A2.9	Glomerular filtration rate (eGFR) < 60 mL/min/1.73m ² at screening or expected during trial	Exclusion criterion 10 met	None
A2.10	ALT or AST > 2x ULN or total bilirubin > 1.5x ULN	Exclusion criterion 11 met	None
A2.11	Excluded medical condition	Exclusion criteria 12, 13, 14, 15, 16 or 23 met	None
A2.12	Significant substance abuse	Exclusion criterion 17 met	None

Table 6.2: 1 Important protocol violations (cont.)

Category / Code	Description	Comment	Excluded from
	A2.13	Hypersensitivity to trial drug or allergy to fluorescein dye	Exclusion criterion 18 met
	A2.14	Major surgery performed within 12 weeks prior to randomization or planned during trial	Exclusion criterion 19 met
	A2.15	Current enrollment in, or < 30 days or 5 times half-life of the investigational drug since participating in, another investigational drug trial	Exclusion criterion 20 met
	A2.16	Previous randomization in this trial	Exclusion criterion 21 met
	A2.17	Women who are pregnant, nursing, or who plan to become pregnant during the trial	Exclusion criterion 22 met
B	Informed consent		
	B1	Informed consent not available/not done	Inclusion criterion 8 not met; informed consent date or signature missing
	B2	Informed consent given late	Study informed consent date after date of any study-related procedure; biobanking informed consent date after sample collection date; or re-consent given late.
C	Trial medication and randomisation		
C1	Incorrect trial medication taken		
	C1.1	No study medication taken	Patient randomized but no evidence of study medication taken
	C1.2	Incorrect trial medication taken	Incorrect medication taken for >20% of treatment duration or > 20% of last dose interval before primary endpoint assessment as identified after database lock by comparison of assigned drug kit number from IRT with drug kit number recorded in eCRF. [manual review]
C3	Non-compliance		
	C3.1	Non-compliance with trial medication	Mean overall treatment compliance across treatment duration for an individual <80% or >120%.
C4	Medication code broken		
	C4.1	Medication code broken at site without just cause	Medication code broken for reasons other than those documented in CTP Section 4.1.5.2. [manual review]

Table 6.2: 1 Important protocol violations (cont.)

Category / Code		Description	Comment	Excluded from
D		Concomitant medication		
	D2	Use of prohibited concomitant medication	Reported use of prohibited concomitant medications, defined in CTP Section 4.2.2.1[manual review]	PPS
F		Trial specific		
	F1.1	Study eye incorrectly selected.	Ophthalmologic data and/or issues report indicates study eye incorrectly selected. Incorrect study eye based on DRSS and BCVA will be flagged via SAS code. Manual review is needed to confirm protocol violations.	None
	F1.2	Study eye incorrectly selected – Confirmed	Incorrect selection of study eye identified in F1.1 and confirmed by manual review.	PPS
	F2	Imaging performed by non-certified personnel.	Manual review of issues report identified non-certified personnel performing imaging.	PPS
	F3	Imaging performed using non-certified equipment.	Manual review of issues report noted use of non-certified imaging equipment.	PPS
	F4	BCVA/CS performed by non-certified personnel.	Manual review of issues report identified non-certified personnel performing BCVA/CS assessment.	PPS
	F5	BCVA/CS performed using non-certified equipment.	Manual review of issues report noted use of non-certified BCVA/CS equipment.	PPS

Note: Missing visits, evaluations, and tests will be considered missing data, not protocol deviations.

